- Correlation of ^{89}Zr -Df-IAB22M2C (CD8 PET Tracer) uptake in biopsied tumors as determined by SUV-based quantitative measures :SUVmax, SUVpeak, SUVmean, CD8 tumor volume (volume of tumor tissues with increased CD8 uptake with SUV > 40% SUVmax), and Tumor: Reference ratios with CD8+ cell measurements as determined by IHC from biopsy samples.

Secondary Outcome Measures:

- Assessment of Baseline and On-Treatment ^{89}Zr -Df-IAB22M2C (CD8 PET Tracer) uptake and distribution in tumors and lymphoid organs, and measurement of change between the paired observations, as determined by:
 - Tumor uptake analysis as described by visual scoring scales
 - Lymph node chain visibility defined as location and number of nodes in lymph node chains identified with elevated ^{89}Zr -Df-IAB22M2C (CD8 PET Tracer) activity.
- Assessment of Baseline and On-Treatment ^{89}Zr -Df-IAB22M2C (CD8 PET Tracer) uptake and distribution in tumors and lymphoid organs and measurement of change between the paired observations, as determined by:
 - SUV-based quantitative analysis: SUVmax, SUVpeak, SUVmean, CD8 tumor volume (volume of tumor tissues with increased CD8 uptake with SUV > 40% SUVmax), and Tumor: Reference ratios
 - Visual and SUV-based quantitative analysis (SUVmax, SUVpeak, SUVmean) in tumor and reference tissues including lymph nodes, spleen and bone marrow.
- Measurement of change in ^{89}Zr -Df-IAB22M2C (CD8 PET Tracer) uptake in biopsied tumors as determined by SUV-based quantitative analysis : SUVmax, SUVpeak, SUVmean, CD8 tumor volume (volume of tumor tissues with increase CD8 uptake with SUV > 40% SUVmax) and Tumor: Reference ratio from Baseline to On-Treatment PET scans and correlation with change in CD8+ cells as determined by IHC from biopsy samples obtained prior to and 4 to 7 weeks after the start of immunotherapy.
- Description of biodistribution patterns of ^{89}Zr -Df-IAB22M2C (CD8 PET Tracer) on PET_{baseline} and PET_{Tx} and any changes in biodistribution between baseline and On-Treatment.

Exploratory Outcome Measures:

- Correlation of visual and quantitative ^{89}Zr -Df-IAB22M2C (CD8 PET Tracer) uptake in tumor lesions with change in CD8+ cells as determined by IHC from biopsy samples obtained prior to and 4 to 7 weeks after the start of immunotherapy.
- Estimation of positive predictive value, negative predictive value, sensitivity and specificity of ^{89}Zr -IAB22M2C (CD8 PET Tracer) PET for detecting CD8+ cells as determined by IHC.

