Protocol Number: IAB-CD8-201	Indication: Patients with Selected Advanced and Metastatic Solid Tumors including Melanoma, Non-Small Cell Lung Cancer, Renal Cell Carcinoma, Squamous Cell Carcinoma of the Head and Neck, Colorectal Cancer-MSI high, Triple Negative Breast, Bladder, Cervical, and Esophagogastric Cancers

PET Tracer) and its associated PET/CT scan; and within 2 weeks after 2nd infusion of ^{89}Zr-Df-IAB22M2C (CD8 PET Tracer) and its associated PET/CT scan.
 
 • If biopsy will be performed after the PET/CT scan (either Baseline or On-treatment), image guided biopsy will be the preferred method, where the lesion is chosen based on CD8+ PET signal on the CD8 PET/CT scan. • The need for the Baseline biopsy will be considered on a case by case basis following discussion with the Sponsor. • If a patient has had a diagnostic biopsy within 2 months (60 days) prior to the 1st infusion of ^{89}Zr-Df-IAB22M2C (CD8 PET Tracer), the archival tissue can be submitted for IHC analysis, with approval of the Sponsor, provided the specimen is of adequate quality and the biopsy was obtained from a lesion that is RECIST 1.1 measurable and remains visible on conventional imaging with CT/MRI. If these conditions are met, then the patient can be exempt from the Baseline biopsy. • Archival tumor tissue must have been obtained after last systemic therapy. The lesion from which the archival tissue is obtained should not have received radiation post-biopsy. • For the 2nd biopsy (within 2 weeks after 2nd infusion of ^{89}Zr-Df-IAB22M2C [CD8 PET Tracer] and PET/CT scan), optional surgical resection may be performed in place of biopsy if investigator determines the tumor as resectable. • Assuming a correlation between Tumor SUVmax to SUVmean Aorta reference tissues and CD8+ cell measurements by IHC of 0.65, 47 patients will be needed to obtain a width of 0.30. The 95% confidence interval is 0.47-0.78, which would be in the range of a good correlation. 	

Name of Sponsor/Company: ImaginAb Inc. Name of Study Product: ⁸⁹ Zr-Df-IAB22M2C	
Protocol Number: IAB-CD8-201	Indication: Patients with Selected Advanced and Metastatic Solid Tumors including Melanoma, Non-Small Cell Lung Cancer, Renal Cell Carcinoma, Squamous Cell Carcinoma of the Head and Neck, Colorectal Cancer-MSI high, Triple Negative Breast, Bladder, Cervical, and Esophagogastric Cancers
Inclusion Criteria:	

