All collected study data will be presented in subject data listings. Statistical analyses will be performed using SAS® for Windows, version 9.4 or later. Descriptive statistics (n, mean, standard deviation, median, minimum and maximum) will be presented for continuous variables. Frequencies and percentages will be presented for categorical variables.

Sample Size Determination and Rationale

The sample size calculation is based on the co-primary outcome measure of correlation of ^{89}Zr -Df-IAB22M2C (CD8 PET Tracer) uptake as determined by Tumor SUVmax to SUVmean Aorta reference tissue with CD8+ cell measurement as determined by IHC from biopsied lesions. Since there are no validated comparator studies or imaging scans that can serve as reference values scans for CD8+ cell count, the objective of this study is to estimate the correlation between CD8+ cells and quantitative uptake by PET with sufficient precision.

The objective is to estimate the Spearman's correlation coefficient with a 0.30 width (width of the 95% confidence interval calculated based on Bonett and Wright (2000) method). The sample size is adjusted for intra-patient correlation assuming two observations per patient (baseline and on-treatment) and a moderate intra-patient correlation of 0.30 (plausible as patients will receive treatment between the two observations). Assuming a correlation between Tumor SUVmax to SUVmean Aorta reference tissue and CD8+ cell measurements of 0.65, 47 patients will be needed to obtain a width of 0.30. The 95% confidence interval is 0.47-0.78, which would be in the range of a good correlation. If the estimated correlation is 0.75, the 95% confidence interval becomes 0.61-0.85 (width = 0.24). If the estimated correlation is 0.50, the 95% confidence interval becomes 0.29-0.66 (width = 0.37).

Analysis Populations

Efficacy population

The efficacy population is defined as all subjects who have received at least one dose of study imaging agent and have at least one CD8 PET scan of adequate quality and corresponding core biopsy samples of adequate quality from at least one location.

For correlating treatment-related change in PET signal with change in CD8+ cell measurements on IHC: Efficacy population is defined as all subjects who have paired Baseline and On-treatment CD8 PET scans and corresponding paired biopsy samples.

Per Protocol (PP) Population

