The Per Protocol (PP) population is defined as the set of subjects who meet the efficacy population requirements and were not associated with a major protocol violation. This population will be identified before the database lock.

Safety Population

The Safety population is defined as all subjects receiving at least one dose of the study imaging agent.

Analysis Methods:

The primary analysis of the primary and secondary outcome measures will be conducted using the PP population. Analyses of safety outcomes will be conducted using safety population.

Safety Analysis:

Analyses of safety outcomes will be conducted using the safety population.

Adverse events will be coded using MedDRA. Treatment Emergent AE's (TEAE) are defined as events with an onset on or after the first treatment. TEAEs will be summarized by treatment group and by stage of the study, System Organ Class, and preferred term. The following TEAE summaries will be provided:

- TEAEs by severity grade
- TEAEs by relationship to study treatment.

Name of Sponsor/Company: ImaginAb Inc. Name of Study Product: ^{89}Zr -Df-IAB22M2C	
Protocol Number: IAB-CD8-201	Indication: Patients with Selected Advanced and Metastatic Solid Tumors including Melanoma, Non-Small Cell Lung Cancer, Renal Cell Carcinoma, Squamous Cell Carcinoma of the Head and Neck, Colorectal Cancer-MSI high, Triple Negative Breast, Bladder, Cervical, and Esophagogastric Cancers

In addition, separate summaries of serious adverse events, and adverse events resulting in discontinuation of study treatment will be presented.
 
The first co-primary objective is the evaluation of the safety of repeat doses of ^{89}Zr-Df-IAB22M2C (CD8 PET Tracer). Adverse events will be graded using CTCAEv5. All grades will be tabulated overall and by injection number (1st injection vs 2nd injection). Considering that the safety profile of one dose has been established before, no severe (grade ≥ 3) events are expected, but safety will be closely monitored and safety data will be reviewed by a data safety committee.
 
In addition, all the data from physical examination, 12-Lead ECG, Serum chemistry, hematology, and vital signs will also be descriptively summarized.
	

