
Efficacy Analysis:
 
The primary analysis of the primary and secondary outcome measures will be conducted using the PP population.
 
For the efficacy outcome measures, the data will be summarized and compared according to the variable type. Continuous data summaries will include:
 
 Descriptive summary of number of observations, mean, standard deviation, median, 1st and 3rd quartile and minimum and maximum values. Inferential statistics include: 
 Pearson correlations T-test or ANCOVA using the baseline value as a covariate, if the Normality assumption is met non-parametric or rank based analysis, if the Normality assumption is not met. 
Categorical data summaries will include:
 
 Frequency counts and percentages. Chi square test or Logit model for inferential statistics. 
To establish the relationship of the PET/CT uptake with CD8+ cells (the second co-primary objective), the main analysis will be the Spearman's correlation coefficient between Tumor SUVmax to Aorta reference tissue and CD8+ cells value at all times (baseline and post-treatment). The correlation will then be estimated using SUVpeak, SUVmean, CD8 tumor volume (defined as the volume of tumor tissue with SUV $> 40\%$ of SUVmax), and other tumor: reference ratio. The correlation will be given with a two-sided 95% confidence interval accounting for clustering with subjects as clusters (as most subjects will have measurements at 2 times). Those analyses will be repeated separately at baseline and post-treatment as exploratory analyses.
 
The first 15 to 20 patients might be described during the study in order to check the technical quality of the data and the imaging. This description will not allow for stopping the trial, no statistical inference will be done, and therefore no type-I error is spent at this stage.

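### PET-only secondary outcomes are analysed in the PP set, so subjects with good scans but no adequate corresponding tissue at either visit are left out

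*Combined protocol and SAP*

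**What the plan says.** The rule comes from three statements in the synopsis.

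- **Analysis Methods and Efficacy Analysis:** "The primary analysis of the primary and secondary outcome measures will be conducted using the PP population". No secondary outcome is exempted.
- **Per Protocol (PP) Population:** "the set of subjects who meet the efficacy population requirements and were not associated with a major protocol violation".
- **Efficacy population:** dosed subjects who "have at least one CD8 PET scan of adequate quality and corresponding core biopsy samples of adequate quality from at least one location". A separate paired-scan, paired-biopsy definition follows, but it serves only the correlation of PET change with IHC change.

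The one set without a tissue requirement is the Safety population, "The Safety population is defined as all subjects receiving at least one dose of the study imaging agent", and it is assigned to safety outcomes.

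Under Secondary Outcome Measures, most items are read from images alone. They are visual tumor scores, lymph node chain visibility, SUV measures "in tumor and reference tissues including lymph nodes, spleen and bone marrow", change between the paired scans, and biodistribution. Only the correlation of change in uptake with change in CD8+ cells needs tissue.

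Under Tumor Biopsy, the plan allows for tissue to be absent or to take another form. On the first biopsy: "The need for the Baseline biopsy will be considered on a case by case basis following discussion with the Sponsor". Sponsor-approved archival tissue, taken up to 60 days before the first tracer infusion, may replace it. For the second visit, "optional surgical resection may be performed in place of biopsy if investigator determines the tumor as resectable".

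**The concern.** Spleen uptake or whole-body biodistribution on a good scan is equally valid whether or not a tumor core was adequate. The analysis set nevertheless makes tissue a condition of entry for outcomes that do not use it. A subject can follow the protocol, complete two good scans and still be left out, for example when the baseline biopsy is waived and the second is inadequate or not done.

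Two things are at stake. The first is the loss of scans already acquired and read. The second is possible selection: having no usable tissue at all may depend on how accessible the lesions are, on response, or on the patient's condition, and these may also relate to uptake or its change.

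**Working it through.** **1. Who is in and who is out.** Secondary outcomes lead to PP, PP leads to the efficacy population, and that leads to one adequate scan with corresponding adequate core biopsy samples. For a subject with two good scans and no major violation:

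| Baseline tissue | On-treatment tissue | In PP? |
|---|---|---|
| adequate | adequate | yes |
| adequate | none or inadequate | yes |
| waived or inadequate | adequate | yes |
| waived or inadequate | none or inadequate | **no** |

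Only the last row is lost. A rarer route to exclusion is baseline tissue whose own scan is inadequate, followed by a good on-treatment scan without tissue: no scan then has a corresponding biopsy.

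**2. The plan's own figure, and whether it depends on this.** Inputs from Sample Size Determination and Rationale: 47 patients, 2 observations each, intra-patient correlation 0.30, Spearman correlation 0.65, Bonett-Wright 95% interval.

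- Design effect = 1 + (2 - 1) × 0.30 = 1.30. Effective n = 47 × 2 / 1.30 = 72.3.
- SE on the Fisher z scale = sqrt[(1 + 0.65²/2) / (72.3 - 3)] = 0.132.
- Interval = tanh[atanh(0.65) ± 1.96 × 0.132] = 0.475 to 0.776, width 0.301. The plan states 0.47-0.78 and 0.30.

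The figure reproduces. It concerns the PET-IHC correlation, which needs tissue, so a PET-only analysis set leaves N = 47 unchanged.

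**3. Expected loss.** The documents give no biopsy failure rate. Assume a share p of biopsies is unusable at each visit, that the two visits are independent, and that all 47 subjects have evaluable scans. Subjects lost = 47 × p². The interval for a subject-level mean widens by the factor 1/sqrt(1 - p²).

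| p | Share lost (p²) | Subjects lost of 47 | Interval factor |
|---|---|---|---|
| 0.15 | 2.25% | 1.1 | 1.01 |
| 0.20 | 4.0% | 1.9 | 1.02 |
| 0.30 | 9.0% | 4.2 | 1.05 |

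**4. If failures cluster.** The same inaccessible lesion can spoil both biopsies. With an assumed within-subject correlation of 0.3 between failures, the share lost is p² + 0.3 × p(1 - p).

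- p = 0.15: 0.0225 + 0.3 × 0.1275 = 0.061, or 2.9 subjects; factor 1/sqrt(0.939) = 1.03.
- p = 0.30: 0.09 + 0.3 × 0.21 = 0.153, or 7.2 subjects; factor 1/sqrt(0.847) = 1.09.

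**The case against.** The strongest reply is that few subjects are affected and little hangs on it.

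- **Double failure is limited by design.** Inclusion criterion 2 requires an accessible lesion eligible for biopsy, criterion 7 requires willingness to undergo all procedures, 3 to 5 cores are preferred, and archival tissue can stand in at baseline. This stands, and it supports a low estimate.
- **The obvious bias mechanism is weakened.** Shrinking lesions and declining patients mainly affect the second biopsy. Losing that one alone removes nobody who has baseline tissue with an adequate baseline scan. This stands too: selection works only through subjects who also lack usable baseline tissue.
- **The consequence is modest.** The only interval specified under Efficacy Analysis is for the correlation. PET-only outcomes get summaries and generic tests. All data are listed, and supplementary summaries are not barred. True, but a listing is not an analysis, and no other set is named for these outcomes.
- **The available text is essentially the synopsis**, which points to a fuller section for the schedule and assessments. The absence of an exemption is established only for what can be read.

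A reader might infer two stronger things. One is that anyone who misses or declines a biopsy is removed; the efficacy definition contradicts this, since one adequate scan-biopsy pair at either visit suffices. The other is a loss of about 6 to 9 of 47 subjects (13-19%), reached by adding 10% (4.7 subjects) whose sole major violation concerns biopsy to the 1.1-4.2 above. The available text neither gives that rate nor defines a major violation. A sponsor-agreed waiver is permitted conduct, and the two groups could overlap. That figure should not be used.

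**Conclusion.** The mismatch between outcome and analysis set is real and explicit. Tissue-free secondary outcomes are restricted to subjects with at least one adequate scan-biopsy pair and no major violation, and nothing in the available text exempts them.

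The effect is small under the stated assumptions: about 1-4 of 47 subjects (2-9%) and intervals about 1-5% wider with independent failures, or about 3-7 subjects and 3-9% wider with the assumed clustering. Subjects missing one biopsy would add to this only if the miss were ruled a major violation, and that number cannot be estimated. Selection bias in the reported change in uptake is possible, but the documents support neither a size nor a direction for it.

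The point is worth acting on because the remedy is nearly free and removes selection on biopsy success from results that do not need tissue.

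**What to change.** 1. In Analysis Populations, define a PET-evaluable set: all dosed subjects with an evaluable CD8 PET scan, whatever their biopsy status, excluding only violations that affect the scan. Require both scans for change outcomes.
2. In Analysis Methods and Efficacy Analysis, assign the PET-only secondary outcomes to this set. Keep the existing biopsy-based sets for every outcome that uses IHC.
3. As a minor alignment, reword the core-biopsy requirement in the efficacy population to cover the tissue that Tumor Biopsy already accepts: core biopsy, approved archival tissue, or surgical resection. Read literally, the present wording leaves out a subject whose only usable tissue is a resection. Unlike items 1 and 2, this touches the IHC analyses, where it could only add subjects.

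The cost is a few sentences. It needs no new scans, reads or visits, and no change to N = 47. Items 1 and 2 leave the co-primary correlation as it is.

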Trial Design: 
 Eligible subjects who meet Inclusion/Exclusion criteria will receive ^{89}Zr-Df-IAB22M2C (CD8 PET Tracer) as an IV infusion within 1 week prior to the onset of immunotherapy, and 4 to 6 weeks after start of immunotherapy. Conventional CT Chest, Abdomen and Pelvis (including Neck for SCCHN subjects) or MRI or whole body ^{18}FDG-PET scan will be performed within 45 days prior to 1st infusion of ^{89}Zr-Df-IAB22M2C (CD8 PET Tracer). Fresh tumor biopsy (Preferred3 to 5 core biopsies) will be performed at: 
 Baseline: within -28 to -7 days prior to 1st infusion or 0-6 days after 1st infusion of ^{89}Zr-Df-IAB22M2C (CD8 PET Tracer) and its associated PET/CT scan of ^{89}Zr-Df-IAB22M2C (CD8 PET Tracer) at 24hrs post injection. Within 2 weeks after 2nd infusion of ^{89}Zr-Df-IAB22M2C (CD8 PET Tracer) and its associated PET/CT scan at 24 hrs post injection. Archival tumor biopsy tissues obtained within 2 months (60 days) prior to 1st infusion of ^{89}Zr-Df-IAB22M2C (CD8 PET Tracer) may be submitted in place of Baseline fresh biopsy, with approval from the Sponsor. PET/CT scans (PET_{baseline} and PET_{tx}) will be obtained at 24 \pm 3 hours after each infusion of ^{89}Zr-Df-IAB22M2C (CD8 PET Tracer). Anti-drug antibody (ADA) blood samples will be collected at the following time points: at Baseline, prior to receiving the 2nd infusion of ^{89}Zr-Df-IAB22M2C (CD8 PET Tracer), and at End-of-Study safety follow-up visit. Safety follow-up: 4-6 weeks after the last dose of ^{89}Zr-Df-IAB22M2C (CD8 PET Tracer). Extended follow-up: collect Standard of Care (SOC) imaging only, up to 12 months after start of immunotherapy. 	
The detailed study schedule and assessments in each visit are provided in Section Error! Reference source not found. of the protocol.	
Tumor Biopsy: 
 Fresh tumor biopsy from a RECIST 1.1 measurable lesion (excluding cutaneous lesions) within -28 to -7 days prior to 1st infusion immunotherapy or 1 to 6 days after 1st infusion of ^{89}Zr-Df-IAB22M2C (CD8 	

Name of Sponsor/Company: ImaginAb Inc. Name of Study Product: ^{89}Zr -Df-IAB22M2C	

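### For categorical efficacy outcomes the plan names only a chi-square test or logit model, although the secondary categorical outcomes compare two visits of the same subjects

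*Combined protocol and SAP*

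**What the plan says.** The Secondary Outcome Measures in the synopsis cover visual scoring of tumor uptake, lymph node chain visibility (location and number of nodes) and SUV measures. Each is assessed at baseline and on treatment, with "measurement of change between the paired observations, as determined by" the listed measures. There is one group: under Trial Design all eligible subjects receive the same tracer, before and after the start of immunotherapy.

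The Efficacy Analysis section gives a single list of methods for the efficacy outcomes, where "the data will be summarized and compared according to the variable type":

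- Continuous data: Pearson correlation, then "T-test or ANCOVA using the baseline value as a covariate, if the Normality assumption is met", otherwise an unnamed rank-based method.
- Categorical data: counts and percentages, then "Chi square test or Logit model for inferential statistics".

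No method is tied to a named secondary outcome, and no paired or repeated-measures method is named for categories. Within-subject dependence is addressed for the co-primary Spearman correlation and its alternative SUV versions, whose interval is to be given "accounting for clustering with subjects as clusters (as most subjects will have measurements at 2 times").

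**The concern.** The sample size section assumes an intra-patient correlation of 0.30, and the co-primary interval is adjusted for it. For the secondary comparisons of the same two visits, the list offers categorical methods which, in their ordinary form, assume independent observations. When the two visits are positively correlated, the chi-square test overstates the variance of the difference between visits. It then rejects too rarely when nothing has changed, and misses changes that a paired test would find.

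A second gap pulls the other way. A subject may have several tumors and nodes, and no unit of analysis is given for the secondary outcomes. If lesions were entered as independent rows, the variance of the mean change would be understated and changes in uptake would be declared too often. What is at stake is the trial's secondary statements on whether tracer uptake changes under immunotherapy.

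**Working it through.** **1. The plan's own figure.** Sample Size Determination gives 47 patients, two observations each, intra-patient correlation 0.30, Spearman correlation 0.65 and the Bonett-Wright interval. The design effect is 1 + (2 − 1) × 0.30 = 1.3, so there are 94 / 1.3 = 72.3 effective observations. The interval is tanh(atanh(0.65) ± 1.96 × √[(1 + 0.65²/2) / (72.3 − 3)]) = tanh(0.775 ± 0.259) = 0.475 to 0.776, which matches the stated 0.47 to 0.78. A width of at most 0.30 needs 73 effective observations, and 73 × 1.3 / 2 = 47.45. The sample size reproduces, and nothing below changes it.

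**2. Chi-square on paired categories, type I error.** Inputs: 47 pairs (the planned number, so an upper limit), a binary score cut from a latent normal variable, and latent correlation ρ between visits. The documents give no correlation for visual scores. The value 0.30 is borrowed from the sample size section, and 0.50 is an assumption.

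With half the subjects positive at each visit, the correlation of the binary scores is φ = (2/π) × arcsin(ρ), and the true type I error is 2 × [1 − Φ(1.96 / √(1 − φ))].

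- ρ = 0.30: φ = 0.194, and 1.96 / √0.806 = 2.18, giving 2.9%. Simulation gives 2.7% to 2.9% (McNemar about 5.2%).
- ρ = 0.50: φ = 0.333, and 1.96 / √0.667 = 2.40, giving 1.6%. Simulation agrees (McNemar 4.8% to 4.9%).

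**3. Chi-square on paired categories, power.** Assume a shift from 40% to 60% positive. The chi-square standard error is √(2 × 0.25 / 47) = 0.103, so the rejection limit is 1.96 × 0.103 = 0.202. That is almost exactly the assumed shift of 0.20, so power stays just under one half whatever the correlation.

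McNemar uses √(discordant share / 47) instead. The share positive at both visits is 0.285 at ρ = 0.30 and 0.316 at ρ = 0.50, from the bivariate normal.

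- ρ = 0.30: the discordant share is 0.115 + 0.315 = 0.430, and the limit is 1.96 × √(0.430 / 47) = 0.187. The sampling SD is √[(0.430 − 0.04) / 47] = 0.091, giving power of about 0.55.
- ρ = 0.50: the discordant share is 0.084 + 0.284 = 0.368, the limit is 0.173 and the SD is 0.084, giving power of about 0.63.

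The normal approximation is rough with so few discordant pairs. Simulated power is:

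| Latent correlation | Chi-square | McNemar |
|---|---|---|
| 0.30 | 0.49 to 0.50 | 0.58 |
| 0.50 | 0.49 | 0.65 |

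**4. Continuous measures, only if the t-test were run unpaired.** True type I error is 2 × [1 − Φ(1.96 / √(1 − ρ))]. At ρ = 0.30, 1.96 / √0.70 = 2.34, giving 1.9%. A change that the paired test detects with 80% power would be detected with about 68%.

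**5. Several lesions per subject, only if entered as independent rows.** For m lesions and intraclass correlation ICC of the change, type I error is 2 × [1 − Φ(1.96 / √(1 + (m − 1) × ICC))]. Both m and ICC are assumptions; the documents give neither.

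| Lesions | ICC 0.1 | ICC 0.3 | ICC 0.5 |
|---|---|---|---|
| 2 | 6.2% | 8.6% | 11.0% |
| 3 | 7.4% | 12.1% | 16.6% |
| 5 | 9.8% | 18.6% | 25.8% |

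**The case against.** A reader might infer that the plan prescribes unpaired tests for all secondary change outcomes, that its ANCOVA has no possible use, and that the secondary p-values will therefore be wrong. The documents do not support this:

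- The plan never says unpaired. The t-test may be a paired test, and the rank-based analysis may be a signed-rank test. The outcome list itself calls the observations paired.
- The list is generic. Chi-square, logit and ANCOVA would be ordinary choices for between-subject questions, such as uptake by RECIST response among the Exploratory Outcome Measures. A single-arm trial can still have subgroups.
- Not every secondary outcome is a visit comparison. One correlates change in uptake with change in CD8+ cells, in a population where "Efficacy population is defined as all subjects who have paired Baseline and On-treatment CD8 PET scans and corresponding paired biopsy samples", and biodistribution is only described.
- With one change value per subject, no clustering adjustment is needed. Node visibility can be a count per subject, which would not call for a categorical test at all.
- The power gain is modest at a correlation of 0.30: 9 points with the asymptotic McNemar test, and none with the exact version (0.48).
- No alpha, power or hypothesis is set for the secondary outcomes, the trial aims at estimation, and the text is at synopsis level.

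All of this stands, and it limits the point. It does not remove the categorical gap. The secondary outcomes fall under this list, and the only categorical test it names takes independent samples. A logit model could be made to respect the pairs, but the plan does not say so.

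**Conclusion.** The point holds for categorical comparisons between visits. Followed as written, an ordinary chi-square test is conservative (type I error about 2.8% at latent correlation 0.30 and 1.6% at 0.50) and gives up about 9 to 16 points of power to the asymptotic McNemar test. These figures assume 47 complete pairs, a binary score and a shift from 40% to 60%. The plan expects most rather than all subjects to have two measurements, so there may be fewer pairs and lower power for both tests.

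For continuous measures and for several lesions per subject, the finding is missing specification, not a demonstrated error. Leaving out the pairing is conservative; leaving out lesion clustering is anti-conservative (about 6% to 26% over the assumed range). Neither arises under a paired analysis with one value per subject, which the text permits. Severity is moderate: secondary conclusions are affected, while the co-primary correlation and N = 47 are not.

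**What to change.** In the Efficacy Analysis section, separate visit comparisons from between-subject comparisons.

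- **Categorical, baseline against on-treatment:** replace chi-square/logit with McNemar (binary) or Stuart-Maxwell (more than two categories) where each subject has one score, and say whether McNemar is asymptotic or exact. Where several lesions per subject are scored, use a GEE logit model clustered on subject.
- **Continuous, baseline against on-treatment:** state that the t-test and rank test are the paired t-test and signed-rank test on one change value per subject. For lesion-level data, use a model with subject as the cluster.
- **Unit of analysis:** state for each secondary outcome whether it is the subject, lesion or node.
- **Between-subject comparisons, such as response groups:** keep chi-square, logit and ANCOVA, and name the factor compared.

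The cost is a few lines of text and slightly more programming. No extra patients or procedures are needed. Intervals for lesion-level results will be wider than those from an analysis that ignores the subject.
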